6.3.6 Hypertension.....	17
6.3.7 Electrocardiogram (ECG) and Cardiac Function	18
6.4 Pharmacokinetics/pharmacodynamics	18
6.5 Biomarker evaluation.....	18
7. Document history and changes in the planned statistical analysis	19
8. References	20

Statistical Analysis Plan

BAY 80-6946 / 17322

Page: 3 of 20:

Abbreviations

AE	Adverse event
ATC	Anatomical-Therapeutic-Chemical
CRF	Case report form
CSR	Clinical study report
CTCAE	Common Terminology Criteria for Adverse Events
DMC	Data Monitoring Committee
e.g.	For example, exempli gratia
ECG	Electrocardiogram
ECOG	Eastern Cooperative Oncology Group
eCRFs	Electronic case report forms
EOT	End of treatment
FL	Follicular lymphoma
FLIPI	Follicular Lymphoma International Prognostic Index
GCP	Good Clinical practice
h	Hour(s)
i.e.	That is, id est
ICF	Informed consent form
IgM	Immunoglobulin M
iNHL	Indolent Non-Hodgkin's lymphoma
IV	Intravenous
LPL	Lymphoplasmacytoid lymphoma
M-1	Metabolite 1
M&S	Modeling & Simulation
MALT	Marginal-zone lymphoma of mucosa-associated lymphoid tissue
MedDRA	Medical Dictionary for Regulatory Activities

Statistical Analysis Plan

BAY 80-6946 / 17322

Page: 4 of 20:

mg	Milligram
mmHg	Millimeter of mercury
MUGA	Multiple gated acquisition
NCI	National Cancer Institute
NCI-CTCAE	National Cancer Institute – Common Terminology Criteria for Adverse Events
NHL	Non-Hodgkin's lymphoma
NMZL	Nodal marginal-zone lymphoma
NYHA	New York Heart Association
OEE	Overall extent of exposure
PD	Progressive disease
PK	Pharmacokinetic
PT	Preferred Term
SAC	Statistical Analysis Center
SAE	Serious adverse event
SAF	Safety analysis set
SAP	Statistical analysis report
SAS	Statistical Analysis System
SFU	Safety follow-up
SLL	Small lymphocytic lymphoma
SMZL	Splenic marginal-zone lymphoma
SOC	System Organ Class
TEAE	Treatment-emergent adverse event
TESAE	Treatment-emergent serious adverse event
TFL	Table, figure, listing
WHO	World Health Organization

Statistical Analysis Plan

BAY 80-6946 / 17322

Page: 5 of 20:

WHO-DD WHO Drug Dictionary

WM Waldenström macroglobulinemia

1. Introduction

Indolent NHLs encompass the following low-grade histologic subtypes of B-cell NHL included in the 2008 World Health Organization (WHO) classification of lymphoid neoplasm: follicular lymphoma (FL), small lymphocytic lymphoma (SLL), lymphoplasmacytic lymphoma (LPL), which is defined as Waldenström's macroglobulinemia (WM) when associated with a monoclonal immunoglobulin M (IgM) component and bone marrow involvement, splenic marginal-zone lymphoma (SMZL), nodal marginal-zone lymphoma (NMZL) and marginal-zone lymphoma of mucosa-associated lymphoid tissue (MALT) (1). FL is the second most common subtype of NHL with 25% of newly diagnosed cases (2), followed by MALT lymphoma with 7% of all NHLs, while other subtypes are rather rare, with SLL, LPL, SMZL and NMZL accounting for 3%, 2%, 2% and 1% of NHL patients, respectively.

Indolent NHLs have a relatively good prognosis with a median survival longer than 10 years, but they are incurable with current available therapeutic options, especially in advanced stages. There are no guideline recommendations or widely accepted standards of care for patients beyond first relapse. The treatment given depends on the patient's condition, physician's preference, and availability of drugs not already used in previous lines of treatment. There is therefore a need for drugs with new targets and mechanisms of action that are effective and have a safety profile different from that of drugs used in earlier lines of treatment.

Copanlisib, a small molecule PI3K inhibitor, is a targeted agent that works by controlling the signaling pathway relevant for the survival and proliferation of iNHL cells. It is currently under investigation in various trials enrolling cancer patients and it has been approved for FL in the U.S. The evaluation of copanlisib's anticancer activity via a clinical trial design that controls for the natural history of tumor growth minimizes investigator bias in assessing treatment outcomes.

The original protocol, Version 1.0, is dated 20 MAY 2014. This statistical analysis plan (SAP) v3.0 describes the final analysis for study 17322 and is based on the integrated clinical study protocol Version 6.0 (protocol amendment 6), dated 01 DEC 2017. Following sponsor's decision to stop enrollment due to lack of feasibility to complete this study in reasonable time frame as protocol amendment 5 became effective, limited number of patients will be included in the analyses. The safety analyses will be performed as per the protocol. For other changes please refer to section 7 in this SAP.

2. Study Objective

The primary objective of this study is:

- To assess the safety of copanlisib.

3. Study Design

Initially this was a randomized, double-blind, two-arm Phase III study to evaluate the efficacy and safety of copanlisib as monotherapy in comparison to placebo in patients with rituximab-refractory iNHL. However, following sponsor's decision to stop enrollment on 03 MAR 2017 due to lack of feasibility to complete this study in reasonable time frame, the study design was modified as protocol amendment 6 became effective. All patients on study treatment will be offered to continue treatment with copanlisib after unblinding procedures are completed.

[figure not shown]
Statistical Analysis Plan

BAY 80-6946 / 17322

Page: 7 of 20:

The overview of study periods is presented in [Figure 3–1](#).

[figure not shown]
Figure 3–1 Study Periods

The start of the study period is defined by signing of the informed consent form (ICF).

A graphical presentation of the overall study design as of amendment 5 is shown in [Figure 3–2](#).

Figure 3–2: Overall Study Design

Schedule of procedures is presented in the protocol amendment 6, Table 7–1.

Treatment Period

The start of the treatment period is defined by first administration of study drug (Copanlisib or placebo). Copanlisib will be administered IV over approximately 1h at starting dose of 60 mg on Days 1, 8 and 15 of each 28-day treatment cycle. Treatment will be continued until progressive disease (PD) by radiological assessments or clinical progression (tumor evaluations will be made at intervals that comply with the institution's standard of care [per investigator's assessment]), unacceptable toxicity, or until another criterion is met for withdrawal from the study treatment. Before unblinding, patients in the placebo arm will receive a placebo IV infusion at the same schedule as that of Copanlisib arm. However, when placebo patients had PD before unblinding cut-off, they can choose to switch to Copanlisib and continue to stay in the study.

Disease progression (PD) defined in the Lugano Classification (3) and the Owen criteria (4) for patients with WM will be assessed.

Statistical Analysis Plan

BAY 80-6946 / 17322

Page: 8 of 20:

All patients, after unblinding procedures are completed, will be offered an opportunity to continue this clinical study and receive active treatment with Copanlisib. Patients who are on Copanlisib treatment at the time of unblinding will continue Copanlisib treatment. Patients who are on placebo at the time of unblinding will switch to Copanlisib treatment after unblinding procedures are completed. After individual patient unblinding, patients receiving placebo, who switch to Copanlisib will have all study assessments reset to the initial schedule of study evaluations (i.e. as if the patient was restarted the study at Cycle 1 Day 1).

An End-of-treatment (EOT) visit will be performed within 7 days after the decision is made to discontinue study treatment.

Safety Follow-up Period

Following completion of the EOT visit, patients will enter the Safety follow-up. The Safety follow-up (SFU) visit will take place 30 days (window of +5 days allowed) after the last administration of study drug.

All patients who have already completed the safety follow-up visit at the time the amendment 6 becomes effective will discontinue the study.

4. General Statistical Considerations

4.1 General Principles

Statistical analyses will be conducted by or under the supervision of the sponsor's Study Statistician, except for the analysis of biomarker data, which, if considered to be performed, will be performed by or under the direction of the sponsor's Genomics and Biomarker Statistical Expert. Statistical analyses will be performed by using the software package Statistical Analysis System (SAS) release 9.2 or higher (SAS Institute Inc., Cary, NC, USA).

Due to the decision of stopping enrollment, limited number of patients will be included in the analyses. Therefore, the statistical analyses included in this study will be focused on descriptive statistics on safety variables only. The number of data available and missing data, mean, standard deviation, minimum, quartiles, median, and maximum will be calculated for metric data. Frequency tables will be generated for categorical data.

Definition of safety endpoints, analyses strategies, structure of analyses datasets and layout of analyses data displays are following Bayer standards as documented in the Bayer standard system: Clinical Copanlisib Project Standards, Oncology Therapeutic Area Standards, and Global Medical Standards, respectively. Where the given ordering reflects the priority of the different standards that is specifications of the latter ones have to be followed only if not specified in standards mentioned before. Study-specific specifications may be included in addition to the project standards, if needed.

4.2 Handling of Dropouts

A patient who discontinues study participation prematurely (i.e., prior to disease progression) for any reason is defined as a "dropout" if the patient has already entered treatment.

Patients who drop out will not be replaced.

The number of patients who prematurely discontinue the study and study treatment for any reason, as well as the reasons for premature discontinuation of study treatment, will be reported.

4.3 Handling of Missing Data

In order to achieve the goal of a well conducted clinical trial according to Good Clinical Practice (GCP), every effort should be made to collect all data. However, despite best efforts, it may be inevitable that missing or incomplete data are reported. All missing or partial data will be presented in the patient data listing as they are recorded on the Case Report Form (CRF). Unless noted, missing data will not be estimated or carried forward in any statistical analysis.

The general principle for imputing dates is as follows:

If an adverse event start date is completely missing or partially missing, then it is assumed that the start date occurs at the earliest time on-treatment whenever possible.

If a concomitant medication date is completely missing or partially missing, then the stop date is imputed to maximize the duration of the concomitant treatment. It should be noted that imputation of stop dates only applies to concomitant medications that are not ongoing.

4.4 Interim Analyses and Data Monitoring

No interim efficacy analyses are planned for this study.

A Data Monitoring Committee (DMC) is instituted to maximize the safety of the patients participating in the study. The DMC includes at least three members, including an independent Statistician and Oncologist. Safety review meetings were held as per separate DMC charter.

The report, including tables, listings, and figures, were generated by an independent statistician from a Statistical Analysis Center (SAC). The format and content of these data summaries were specified separately from this study SAP.

Decisions on trial termination, amendment, or cessation of patient recruitment based on risk/benefit assessment were made after recommendations from the DMC have been assessed by the sponsor.

No DMC meeting is planned after the DMC meeting on 21 JUN 2017 with the recommendations that the study can continue with finishing follow-up and there is no need for another safety meeting as this was considered as a close-out meeting.

4.5 Data Rules

If time intervals are to be displayed other than days in statistical evaluations, then one year is considered to have 365.25 days (average length of a year, including leap years), one month is considered to have 30.44 days (average length of a month, including leap years), one week is considered to have 7 days, and one cycle is considered to have 28 days (i.e. 4 weeks).

Baseline

Baseline is defined as the last available measurement performed prior to the first dose of Copanlisib/placebo study drug administration at Cycle 1 Day 1 for the patients who initially received Copanlisib/placebo. For the patients who initially received placebo and switched to Copanlisib after unblinding, baseline is defined as the last available measurement prior to the first dose of Copanlisib after switching.

Repeated measures

Statistical Analysis Plan

BAY 80-6946 / 17322

Page: 10 of 20:

If there are repeated measurements per time point (e.g. laboratory values, vital signs, etc.), the following rules will be used (unless otherwise specified):

- Before the start of the study drug administration (i.e., for screening and baseline value), the latest measurement at scheduled visits will be used. Unscheduled visits will be used, if there are no measurements at pre-baseline or baseline scheduled visits. If the latter is the case, the last unscheduled visit will be used.
- In case of repeated measurements at any post-baseline time point, the first value of the scheduled measurements at that time point will be used. No unscheduled measurements will be used for any time points besides screening / baseline even when measurements at scheduled visits are missing.

5. Analysis Sets

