5.1 Assignment of analysis sets

Full analysis set (FAS)

All patients who were randomized to treatment arms at the start of the study will be included in the FAS. Protocol deviation, demographics, baseline characteristics, medical history, prior and concomitant medication, prior and concomitant anti-cancer therapy will be summarized in the FAS.

Safety analysis set (SAF)

All patients with at least one administration of study drug will be included in the SAF. The SAF will be used for the analyses of study drug exposure, safety and efficacy variables.

All patients with valid pharmacokinetic (PK) data may be analyzed in the evaluation of PK concentrations and parameters.

Patients who signed the informed consent but were not assigned to treatment will be considered screening failures. They will be listed separately.

6. Statistical Methodology

Disposition, protocol deviations, demographics, baseline cancer characteristics, medical history, prior and concomitant medication, prior and concomitant anti-cancer therapy, drug exposure, efficacy and safety variables will be summarized separately for 2 groups including patients

- who were randomized to copanlisib until the end of study (copanlisib group)
- who were randomized to placebo until switching from placebo to copanlisib after PD or after unblinding (placebo group)

Disposition, protocol deviations, concomitant medication, concomitant anti-cancer therapy, drug exposure, efficacy and safety variables will also be summarized separately for patients who switched from placebo to copanlisib.

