6.2 Efficacy

Due to the limited number of patients enrolled in this study, the study efficacy objectives and analyses were removed and the tumor assessment was stopped to be collected since 01 DEC 2017. Summary of tumor response by investigators' assessment will be provided. Progression-free survival and best overall response will also be listed.

Best overall response (BOR)

BOR is defined as the best response per Cheson criteria (ordered CR, PR, SD, PD, NE) and per Owen criteria (ordered CR, very good partial response (VGPR), PR, Minor response(MR),

Statistical Analysis Plan

BAY 80-6946 / 17322

Page: 14 of 20:

SD, PD, NE) over all post-treatment assessments on or prior to the first progression. Tumor assessments after first PD and after start of new anticancer therapy are not considered for best overall response.

Objective response rate (ORR)

ORR is assessed in all patients up to the time of analysis of PFS. ORR is defined as the proportion of patients who have a best response rating over the whole duration of the study (i.e. until time of analysis of PFS) of complete response (CR) or partial response (PR) according to Cheson criteria Lugano Classification and for patients with WM a response rating of CR, very good partial response (VGPR), PR, or minor response (MR) according to Owen Criteria.

Progression-free survival (PFS)

For patients who were randomized to copanlisib until the end of the study and who were randomized to placebo until switching to copanlisib after PD or after unblinding, PFS is defined as the time (in months) from the randomization date to first disease progression or death due to any cause, if death occurs before progression is documented.

For patients who switched from placebo to copanlisib, PFS is defined as the time (in months) from the start date of copanlisib to first disease or death due to any cause, if death occurs before progression is documented.

For details for radiological tumor assessments see protocol section 7.3.2 and for details for tumor assessments in patients with WM see protocol section 7.3.3.

PFS for patients without PD or death at the time of analysis will be censored at the last actual date of tumor assessment or last biochemical assessment for patients with WM without lesions evaluable by imaging.

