6.3.1 Adverse Events

Adverse Events (AEs) will be coded using *Medical Dictionary for Regulatory Activities* (MedDRA) dictionary Version 22.1. Severity of AEs will be graded using the NCI-CTCAE v4.03. AEs will be classified by the investigator as related or not related to study drug.

Treatment emergent adverse events (TEAEs)

TEAEs are defined as any event arising or worsening after start of study drug administration until 30 days (window of +5 days allowed) after the last study drug administration (end of Safety follow-up). More specifically, for the patients who received Copanlisib until the end of study and the patients who received placebo until switching to Copanlisib after PD or after

Statistical Analysis Plan

BAY 80-6946 / 17322

Page: 15 of 20:

unblinding, the start of study drug administration is referring to the start of Copanlisib or placebo after randomization. For the patients switching from placebo to Copanlisib, the start of study drug administration is referring to the start of Copanlisib drug administration after switching. See Section 4.3 for handling of partial dates for AEs. In the case where it is not possible to define an AE as treatment-emergent or not, the AE will be classified by the worst case; i.e. treatment-emergent.

An overall summary of the following TEAEs by MedDRA (SOC) and (PT) will be provided for safety analysis set:

- Any TEAEs
- Any treatment emergent serious adverse events (TESAEs)
- Any TEAEs leading to discontinuation
- Any TEAEs leading to dose modification
- Any TEAEs related to protocol procedure
- Any study drug related TEAEs
- Any study drug related treatment TESAEs
- Any study drug related TEAEs leading to discontinuation
- Any study drug related TEAEs leading to dose modification

The following will be summarized by MedDRA system organ class (SOC) and preferred term (PT), and by worst grade based on Common Terminology Criteria Adverse Event (CTCAE) v. 4.03.

- TEAEs
- TEAEs with incidence $\geq 10\%$
- Grade 3-5 TEAEs
- Treatment related TEAEs
- Treatment related TEAEs incidence $\geq 5\%$
- Grade 3-5 treatment related TEAEs
- TESAEs
- Grade 3-5 TESAEs
- Treatment related TESAEs
- Any TEAEs leading to discontinuation
- Any TEAEs leading to dose interruption
- Any TEAEs leading to dose reduction
- Any drug related TEAEs leading to discontinuation
- Any drug related TEAEs leading to dose interruption
- Any drug related TEAEs leading to dose reduction

Statistical Analysis Plan

BAY 80-6946 / 17322

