6.3.3 Clinical Laboratory Evaluations

Results of the clinical laboratory evaluations (coagulation, hematology, chemistry and urinalysis) by worst CTCAE grade post-baseline will be summarized. Changes in worst grade of laboratory toxicities at last pre-treatment value compared to worst grade post-baseline value is also provided. Worst grades for laboratory toxicities will be calculated according to CTCAE, version 4.03 based on laboratory measurements.

Summary statistics on the values and changes from baseline will also be presented for each quantitative clinical laboratory variable, at each post-baseline visit. For tables displaying

Statistical Analysis Plan

BAY 80-6946 / 17322

Page: 17 of 20:

treatment-emergent laboratory abnormalities, patients with specimen collection between start of treatment and 30 days (window of +5 days allowed) after EOT will be included.

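### SAP Section 4.5 resets baseline for placebo patients who switched after unblinding but not for those who switched after progression, although both are pooled in one switch summary

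*SAP*

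**What the plan says.** Section 4.5 of the SAP gives two baseline rules. The general rule takes the last available value before the first dose of copanlisib or placebo at Cycle 1 Day 1, for patients who initially received either. The second begins: "For the patients who initially received placebo and switched to Copanlisib after unblinding, baseline is defined as" the last available value before the first copanlisib dose after the switch.

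Section 3 (Treatment Period) describes a further way to switch: "when placebo patients had PD before unblinding cut-off, they can choose to switch to Copanlisib and continue to stay in the study". Section 6 treats progression and unblinding as alternative reasons for switching when it defines the placebo group as patients "who were randomized to placebo until switching from placebo to copanlisib after PD or after unblinding (placebo group"). Section 6.2, Section 6.3.1 and Section 7 repeat the pair. Section 6 then makes a single group of all switchers: "efficacy and safety variables will also be summarized separately for patients who switched from placebo to copanlisib".

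The other time origins for that group are not split by route. Section 6.2 states: "For patients who switched from placebo to copanlisib, PFS is defined as the time (in months) from the start date of copanlisib". Section 6.3.1 states, for patients who switch, that "the start of study drug administration is referring to the start of Copanlisib drug administration after switching".

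**The concern.** The switch summary is meant to describe what happens on copanlisib after placebo. That works only if each patient's reference value is taken just before copanlisib. Section 4.5 secures this for one route and is silent on the other, so a patient who switched after progression falls back on the general rule and is referred to a value from before placebo.

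Two inconsistencies would follow. Within the switch group, changes from baseline would have two different starting points. Within a single patient who switched after progression, TEAEs and PFS would start at first copanlisib while changes from baseline would start earlier. Safety is the SAP's stated primary objective and its analyses are descriptive, so these tables will be read at face value. The number of patients is also described as limited, so a few such switchers could move a mean or a shift cell.

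**Working it through.** The SAP gives no figure to reproduce. The check is a comparison of rules.

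**Step 1. Which rule applies to whom**
- *Switched after unblinding:* Section 4.5 names this route. Baseline is the last value before first copanlisib.
- *Switched after progression, before the unblinding cut-off:* Section 4.5 does not name this route, and no other section supplies a reset baseline. The patient initially received placebo, so the general rule applies and baseline is the last value before first placebo.

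**Step 2. Other origins for the same patients**
- *PFS (Section 6.2):* start of copanlisib, both routes.
- *TEAE window (Section 6.3.1):* start of copanlisib, both routes.
- *Baseline (Section 4.5):* start of copanlisib for one route only.

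**Step 3. Outputs in the switch summary that use baseline**
- *Section 6.3.3:* "Summary statistics on the values and changes from baseline will also be presented for each quantitative clinical laboratory variable", at each post-baseline visit.
- *Section 6.3.4:* HbA1c baseline categories, and the shift table from baseline to end of treatment.
- *Section 6.3.5:* vital-sign changes from baseline.

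**Step 4. Form of the effect**

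For a patient who switched after progression:

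change as written = (value on copanlisib − value before copanlisib) + (value before copanlisib − value before placebo).

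With a reset baseline only the first bracket remains. If k of n switchers switched after progression, and d is the mean of the second bracket among those k, the mean change in the switch summary differs by (k/n) × d. The SAP gives none of k, n or d, and d may have either sign, so no number can be attached. If k = 0 the difference is zero. If k = n all switchers share one reference point, so nothing is mixed, but that point still lies before placebo.

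**The case against.** The best defence is that the reference to unblinding in Section 4.5 was meant to include unblinding of a single patient at progression. The study was double-blind, and Section 3 does speak of unblinding patient by patient: "After individual patient unblinding, patients receiving placebo, who switch to Copanlisib will have all study assessments reset", as if restarting at Cycle 1 Day 1. If patients with progression were unblinded individually before choosing copanlisib, the reset rule would cover them. That procedure would normally be in the protocol, which is not at hand.

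This explains how the wording may have arisen but does not settle it. The sentence stands in the paragraph on what happens once study unblinding is complete. The SAP never says that patients switching at progression were unblinded individually, and it repeatedly lists progression and unblinding as alternatives. Since the PFS and TEAE rules cover every switcher, the omission is probably a drafting slip. Even so, two programmers could derive different baselines from this text.

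Other objections stand and limit the point:
- A reader might infer that the grade comparison in Section 6.3.3 is distorted too. That comparison starts from the last value before treatment, not from the defined baseline, and in a switch summary this can mean the last value before copanlisib. It is not clearly affected.
- A reader might infer that the copanlisib and placebo summaries are biased by the omission. They are not: for patients who switched after progression, the general rule gives the right baseline for the placebo period.
- A reader might want a size, for example an HbA1c drift on placebo. The SAP gives no basis for one.
- Merely adding the progression route to the second sentence would not be enough. Section 4.5 attaches baseline to patients rather than to treatment periods, so the longer sentence could be read as replacing the pre-placebo baseline in the placebo-group summary for every switcher.

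**Conclusion.** The point holds as a minor gap in a definition. As written, Section 4.5 leaves patients who switched after progression on a pre-placebo baseline inside a summary where the other switchers, and the PFS and TEAE origins of all switchers, are set at first copanlisib. The outputs exposed are the laboratory changes from baseline, the HbA1c categories and shifts, and the vital-sign changes, in the switch summary only.

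The size is unknown, and it is zero if no patient switched after progression. The conclusion rests on reading the unblinding condition in Section 4.5 as distinct from the progression route, as Section 6 does. A reader might conclude that the reported switch results will certainly mix two baselines. The document does not support that, because it does not show that any such patient exists. No test, error rate or decision rule depends on this baseline.

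**What to change.** Reword the baseline paragraph in Section 4.5 by analysis group:
- *Copanlisib group and placebo group:* the last available measurement before the first dose of randomized study drug at Cycle 1 Day 1.
- *Summary of patients who switched from placebo to copanlisib, whether after progression or after unblinding:* the last available measurement before the first copanlisib dose.

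This gives a switcher one baseline for the placebo period and another for the copanlisib period, and aligns the second with the PFS and TEAE origins already in Sections 6.2 and 6.3.1. The cost is an edit to one short paragraph. It adds no data collection and no analysis; the programming needs only to apply the same derivation to all switchers.

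### SAP 6.3.3 states no exception to the first-scheduled-value rule of 4.5 for its worst-grade laboratory tables; applied there as written, the rule can lower or blank a patient's worst grade but never raise it

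*SAP*

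**What the plan says.** Section 4.5 of the SAP, under repeated measures, sets a rule for the case of several measurements at one time point. It gives laboratory values as its first example and holds unless something else is specified. For repeats after baseline, "the first value of the scheduled measurements at that time point will be used". It then goes further: "No unscheduled measurements will be used for any time points besides screening / baseline even when measurements at scheduled visits are missing".

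Section 6.3.3 plans a table of laboratory results by worst post-baseline CTCAE grade and a shift table: "Changes in worst grade of laboratory toxicities at last pre-treatment value compared to worst grade post-baseline value is also provided". On the derivation it says: "Worst grades for laboratory toxicities will be calculated according to CTCAE, version 4.03 based on laboratory measurements". For tables of treatment-emergent abnormalities, "patients with specimen collection between start of treatment and 30 days (window of +5 days allowed) after EOT will be included". The same section plans summaries of values and changes from baseline at each visit. Nowhere does it say whether repeat or unscheduled values enter the worst-grade and shift tables.

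Section 4.1 places the definition of safety endpoints, the analysis strategies and the dataset structure under sponsor standards that the SAP does not reproduce. It adds: "Study-specific specifications may be included in addition to the project standards, if needed".

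**The concern.** A worst-grade table is meant to show the most severe value a patient reached. The rule in 4.5 suits a by-visit summary, where one value per patient and visit is needed. Carried over to a worst-grade table, it discards repeat and unscheduled samples, and any of these can hold the patient's worst value.

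The stated objective is safety (section 2), and the analyses are descriptive and focused on safety in a limited number of patients (section 4.1). The laboratory worst-grade tables are therefore among the main outputs, and in small groups a single omitted value is visible.

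The direction also runs against the SAP's approach elsewhere. Section 4.3 places an unknown adverse event start date at the earliest possible on-treatment time. Section 6.3.1 counts an event as treatment-emergent when its status cannot be determined. For laboratory grades, the unstated default would lean the other way.

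**Working it through.** The SAP gives no figure to reproduce here: no group sizes, no number of unscheduled draws and no expected rates. The check is therefore of the text, of the direction, and of an illustrative size.

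**1. Text.** Section 4.5 names laboratory values, selects the first scheduled value and bars unscheduled ones after baseline, subject to a stated exception. Section 6.3.3 names the worst post-baseline grade, says that it is graded from laboratory measurements, and includes patients by specimen date. None of these statements says that repeat or unscheduled values are used, so no explicit exception is stated.

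**2. Direction.** For one patient and one toxicity, with baseline held fixed, let S be the grades of the values that 4.5 keeps and U the grades of all other post-baseline values.
- Rule as written: worst grade = max(S).
- All values: worst grade = max(S ∪ U).
- Since S is a subset of S ∪ U, max(S) ≤ max(S ∪ U). If S is empty and U is not, the patient has no gradable value under the rule.

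It follows that the number of patients at or above any grade cannot be higher under the rule than with all values. The pre-treatment side of the shift table follows the separate baseline rule and is not affected.

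**3. Enumeration.** Take two post-baseline time points, each with a first scheduled, a repeat scheduled and an unscheduled value, each graded 0 to 3 or missing. This gives 5^6 = 15,625 patterns, or 15,624 without the all-missing one. Under the 4.5 rule, compared with all values:
- raised: 0
- unchanged: 9,324
- lowered: 6,276
- no gradable value left: 24

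The sum is 9,324 + 6,276 + 24 = 15,624. These counts confirm the direction; they are not probabilities.

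**4. Illustrative size.** Assume a group of n patients, k = 0.3n of them at grade 3 or above on scheduled values, and one further patient who reaches grade 3 only on an unscheduled value. The rule reports k/n and all values give (k+1)/n, so the difference is 1/n whatever k is.
- n = 10: 3/10 = 30.0% against 4/10 = 40.0%, a difference of −10.0 points
- n = 20: 6/20 = 30.0% against 7/20 = 35.0%, −5.0 points
- n = 30: 9/30 = 30.0% against 10/30 = 33.3%, −3.3 points

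The values of n and k and the single affected patient are all assumptions.

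**The case against.** The strongest reply is that 4.5 does not govern these tables. Its rule opens with repeated measurements at a time point and picks one value for that time point, whereas a worst grade spans all time points. Section 6.3.3 sets its own basis (worst grade after baseline, from laboratory measurements, with patients included by specimen date), and this could count as the different specification that 4.5 allows. Section 4.1 also defers to sponsor standards that may contain the record-selection rule. This stands to the extent that the error is conditional. It does not remove the point: the second sentence of the rule does more than choose among repeats, since it bars unscheduled values even where no scheduled one exists, and 6.3.3 never says that such values enter. A programmer could follow either reading.

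A second reply is that the analysis is descriptive and that toxicities reported as adverse events still appear by worst grade in the TEAE tables. This is correct and confines the harm to the laboratory tables. These are planned outputs in their own right, and they could disagree with the TEAE tables for the same patient. Some disagreement can arise under any selection rule, however, because the laboratory grades are calculated from measurements and adverse events are reported separately.

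A third reply is that moving one patient in a group of 10 always gives 10 points. That is so; the illustration shows how sensitive small groups are, not a likely effect in this trial.

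A reader might also infer that patients with only unscheduled samples would leave the denominator, so that percentages could rise. The SAP does not support this: section 5.1 assigns safety variables to the safety analysis set, and 6.3.3 includes patients with a specimen in the window. No smaller denominator is defined.

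**Conclusion.** The point holds as a one-sided risk that the SAP leaves open. If 4.5 is applied to the 6.3.3 tables as written, a patient's worst post-baseline laboratory grade can be lowered or left blank and never raised, and the number of patients at high grades can only fall or stay the same. The direction is certain under that reading, per patient and per toxicity and with baseline held fixed. The size in this trial is unknown; the shifts of 10.0, 5.0 and 3.3 points rest on assumed group sizes and one affected patient.

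A reader might infer that the programmed tables will understate laboratory toxicity. The SAP does not show this. It shows that the written rule permits it and that no sentence in 6.3.3 prevents it.

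**What to change.** Leave 4.5 unchanged and add to 6.3.3: *Notwithstanding Section 4.5, worst post-baseline grade and shift-to-worst-grade tables use all post-baseline laboratory values (scheduled, unscheduled and repeat) within the treatment-emergent period; by-visit summaries follow Section 4.5.* If a sponsor standard already says this, cite it in 6.3.3 instead.

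The cost is one sentence, a footnote, and a changed record selection in the laboratory worst-grade and shift programs. No new data are needed, and the by-visit summaries keep their rule. With the window held fixed, a patient's worst grade can rise and cannot fall. The drawback is that patients with more unscheduled draws have more chances to show a high grade. The footnote should disclose this; it does not remove it.
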